## **6. IMMUNOGENICITY ANALYSIS**

The analysis of immunogenicity will use the PPI set. The most important tables might be repeated on the FA set as a sensitivity analysis.

### **6.1. Parameters**

The following humoral and cellular immune responses will be measured in the different vaccine regimen tested. However not all assays will be available for all immunogenicity analyses covered by this SAP. Further information on which assays will be analyzed in each one of the analysis, will be included in the corresponding DPS documents.

**Immunogenicity against the insert:****Humoral immune response**

- RSV neutralization A strain (titers of neutralizing antibodies).
- RSV F protein enzyme-linked immunosorbent assay (ELISA; pre- and/or post-fusion F antibodies).
- RSV neutralization B and/ or a different A strain (titers of neutralizing antibodies), if available.
- Functional and molecular antibody characterization, if available.

**Cell-mediated immune response**

- Intracellular cytokine staining (ICS, unit: % of subset) or cytokine analysis. Analysis of CD4 and CD8 T-cell subsets and their cytokine expression patterns will be determined by flow cytometry after RSV F-protein peptide stimulation (including, but not limited to CD4/CD8, interleukin-2 [IL-2], IFN $\gamma$ , TNF $\alpha$  and Th1/Th2 subtyping).  
*\*Cytokine analysis for Th1/Th2 profiling will be done in cases where no ICS data can be generated due to insufficient number of PBMCs for ICS assay (see exploratory endpoints below for description)*
- ELISpot IFN $\gamma$  assay (units: SFU/10^6 PBMC). An ELISpot assay is used to quantify the amount of peripheral blood mononuclear cells (PBMCs) able to produce IFN $\gamma$  upon RSV F-protein peptide stimulation, if available.
- PBMC secreted cytokines and ELISpot IFN $\gamma$  are exploratory endpoints and will only be analyzed, if available.
- Cytokine analysis, Cytokine profiles of (in vitro) stimulated PBMC supernatant will be analysed to assess the quantity and quality of the elicited immune responses, including Th1/Th2 balance. Analysis will include, but is not limited to, IFN $\gamma$ , IL-2, IL-4, IL-5, IL-13, and TNF $\alpha$ , if available.

**Immunogenicity against the vector:**

- Adenovirus neutralization assay

This assay assesses neutralizing antibody responses against the Ad26 vectors. This is an exploratory endpoint and will only be analyzed if available.

**6.2. Handling of Missing and/or Unquantifiable Immune Response Data**

Missing immune response data will not be imputed.

Values below the lower limit of quantification (LLOQ) or the provisional cut-off will be treated differently according to the assay:

- Humoral Assays: Values will be imputed based on the type of analysis. For the calculation of the geometric mean titer, values below LLOQ will be imputed to LLOQ/2. While for the calculation of the geometric mean of the increase from baseline, values below LLOQ will be imputed to LLOQ. The LLOQ values per assay are available in the database.
- For ICS assays: no valid LLOQ is available. A provisional cut-off is put at 0.02%. (only for total cytokine response). For the individual cytokine combinations of IFN $\gamma$ , TNF $\alpha$  and IL2, negative values will be imputed with 0. For descriptive statistics or graphs on actual values, values below the cut-off will be imputed to a value of LLOQ/2. For Th1 and Th2, a provisional cut-off of 0.001% is used. These values might change in the future, depending on progressing insight. For descriptive statistics or graphs on actual values, values below the LLOQ will be imputed to a value of LLOQ/2.
- For all assays: values above ULOQ will be imputed with 2xULOQ.

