## 1. INTRODUCTION

This is the Statistical Analysis Plan (SAP) applicable for the VAC18194RSV2001 trial. This SAP is applicable for the following analysis:

- **Cohort 0:** primary analysis will be performed when all subjects have reached Day 57 (28 days post-Dose 2) or discontinued earlier. All available safety and immunogenicity data gathered so far will be included in the analysis; unblinded at the group level.
- **Cohort 1:** interim analysis will be performed when 12 subjects have reached Day 8 or discontinued earlier. All available safety of the 12 subjects and all available immunogenicity data gathered up to that point will be included in the analysis; unblinded at the group level. For the safety analysis snapshot data will be used: there will be no formal cleaning for this analysis. Data will be cleaned in an ongoing basis.
- **Cohort 1:** interim analysis will be performed when at least 12 subjects have reached Day 29 or discontinued earlier. All available safety and all immunogenicity data gathered up to that point will be included in the analysis; unblinded at the group level.
- **Cohort 1:** Depending on the outcome of the first 2 interim analysis of Cohort 1 an additional interim analysis may be performed when at least 24 subjects have reached Day 29 (28 days post-Dose 1) or discontinued earlier. All available safety and immunogenicity data gathered so far will be included in the analysis; unblinded at the group level.
- **Cohort 1:** primary analysis will be performed when all subjects have reached Day 57 (28 days post-Dose 2) or discontinued earlier. All available safety and immunogenicity data gathered so far will be included in the analysis; unblinded at the group level.
- **Final analysis of both cohorts;** at the end of the study, 1 year after the first dose; unblinded.
- Additional interim analyses (blinded or unblinded at the group level) may be performed during the study for the purpose of informing future vaccine-related decisions in a timely manner, or upon health authority request.

This document contains all information needed for performing a full safety and immunogenicity analysis. Tables, listings and figures (TLF) which need to be generated for each analysis will be described in separate data presentation specifications (DPS) document.

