### 6.3.1.2. Cellular assays

For **ICS** and **PBMC secreted** cytokines (if available) analyses may include:

Total Cytokine response: the % of subsets expressing at least IFN $\gamma$ , TNF $\alpha$  or IL2 will be calculated for CD4 and CD8, separately.

Tables with the corresponding descriptive statistics will be provided.

Subject profiles of the actual values over time will be graphically presented.

Actual values are shown as box plots with dots for subject values, and the corresponding median and the first and third quartile (Q1, Q3) per time point for each assay.

In addition, box plots over time, combining the regimens in one graph (without individual subject dots) will also be created.

For all cytokine combinations (IFN $\gamma$  and/or TNF $\alpha$  and/or IL2) pie charts reflecting the distribution of each of the cytokine combinations (the proportion of a specific cytokine combination of the CD4 or CD8 T-cells secreting at least one cytokine) and bar charts reflecting the median magnitude of each combination will be graphically presented. Tables with the corresponding descriptive statistics will be provided.

Th1 and Th2: Th1 is defined as all CD4+ IFN $\gamma$ + and Th2 as all CD4+ IL4+ cells. Subject profiles and graphs of the actual values over time (box-plot type) will be created. In addition, at time points of interest, scatterplots of Th1 vs Th2 might be created.

For the graphs, original values will be displayed on the log10 scale.

The technical details for the calculation of the ICS values to be used in the graphs will be outlined in the DPS.

For **ELISpot**, if available following results will be calculated: N, median, quartiles and range of the actual values will be tabulated and graphically presented.

Tables with the corresponding descriptive statistics will be provided.

Subject profiles of the actual values over time will be graphically presented.

Actual values are shown as box plots with dots for subject values, and the corresponding median and interquartile range per time point for each assay. In addition, box plots over time, combining the regimens in one graph (without individual subject dots) will also be created. For the graphs, original values will be displayed on the log10 scale.

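### SAP 6.2 gives the CD4 total response and the Th1 response nested in it different ICS cut-offs, so Th1 can be reported above its own total, and sets no date after which the cut-offs are fixed

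*SAP*

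**What the plan says.** The ICS bullet of SAP 6.2 opens with "For ICS assays: no valid LLOQ is available". It then sets two thresholds:

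- Total response: "A provisional cut-off is put at 0.02%. (only for total cytokine response").
- Th1 and Th2: "For Th1 and Th2, a provisional cut-off of 0.001% is used".

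For the total, "For descriptive statistics or graphs on actual values, values below the cut-off will be imputed to a value of LLOQ/2". For Th1 and Th2, "For descriptive statistics or graphs on actual values, values below the LLOQ will be imputed to a value of LLOQ/2". Between these rules stands the sentence "These values might change in the future, depending on progressing insight". No date, trigger or parallel reporting goes with it.

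SAP 6.3.1.2 defines the measures. The total is introduced as "Total Cytokine response: the % of subsets expressing at least" one of IFN-gamma, TNF-alpha or IL2, calculated separately for CD4 and CD8. Th1 is every CD4 cell positive for IFN-gamma, and Th2 every CD4 cell positive for IL4.

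SAP 1 schedules group-unblinded analyses before the final one. For the Cohort 1 look at 12 or more subjects at Day 29, the rule is that "all immunogenicity data gathered up to that point will be included in the analysis; unblinded at the group level".

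**The concern.** Every CD4 cell counted as Th1 is also counted in the CD4 total, so Th1 cannot exceed the total in the same sample. Two different cut-offs, each with half-value substitution, do not preserve that order. The total can be pushed down to a fixed low value while its Th1 component is left as measured. The CSR would then hold tables and subject profiles that contradict each other.

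The second issue is timing. With no hypothesis test, the ICS medians, quartiles and plots are themselves the result, and they depend on the threshold. A threshold that can be altered at any time, including after group-level results have been seen, leaves a reader unable to tell whether it was set independently of them. Cohort 1 has 24 active and 12 placebo subjects, so a few samples near a cut-off can matter.

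**Working it through.** The documents state no figure to reproduce here; no power or error rate depends on this rule.

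**Inputs.** Cut-offs of 0.02% (total) and 0.001% (Th1) from SAP 6.2; nesting of Th1 in the CD4 total from SAP 6.3.1.2. Two assumptions are needed. First, LLOQ/2 means half the provisional cut-off, because no ICS LLOQ exists. Second, measured Th1 does not exceed the measured total.

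**Reporting rule.** Let T be the measured CD4 total and H the measured Th1, with H ≤ T.

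- Reported total = T if T ≥ 0.02%, otherwise 0.02%/2 = 0.01%.
- Reported Th1 = H if H ≥ 0.001%, otherwise 0.001%/2 = 0.0005%.

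**Cases.**

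1. T ≥ 0.02%: the total is reported as measured, so there is no inversion.
2. T < 0.02% and H ≤ 0.01%: the total is reported as 0.01% and Th1 as no more than 0.01%, so there is no inversion.
3. 0.01% < H ≤ T < 0.02%: the total is reported as 0.01% and Th1 as H, which is larger. The ratio is H/0.01%, between 1 and 2.

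| Measured T | Measured H | Reported T | Reported H | Ratio H/T |
|---|---|---|---|---|
| 0.015% | 0.012% | 0.010% | 0.012% | 1.2 |
| 0.018% | 0.015% | 0.010% | 0.015% | 1.5 |
| 0.0199% | 0.0199% | 0.010% | 0.0199% | 1.99 |
| 0.025% | 0.015% | 0.025% | 0.015% | 0.6 |

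**With one common cut-off c.** If both values are at or above c, the order is kept. If only H is below, it becomes c/2, which is less than T. If both are below, both become c/2. No inversion is possible. A grid in steps of 0.0001% confirmed none at c = 0.001%, 0.01% or 0.02%.

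**How often.** The documents give no ICS distribution, so this part is assumed: T lognormal with log10 SD 0.4 and median m, and H a share s of T. For a fixed share, inversion needs 0.01%/s < T < 0.02%, so

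P = Φ(log10(0.02/m)/0.4) − Φ(log10((0.01/s)/m)/0.4).

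For s = 0.9 and m = 0.015: Φ(0.312) − Φ(−0.326) = 0.623 − 0.372 = 0.25.

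| Share s | m = 0.005% | m = 0.015% | m = 0.05% |
|---|---|---|---|
| 0.9 | 12.7% | 25.0% | 10.9% |
| 0.7 | 6.1% | 14.4% | 7.3% |
| 0.5 | 0% | 0% | 0% |

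At a fixed share of 0.5 the band is empty, because 0.01%/0.5 = 0.02%. If the share varies between samples the band fills. Simulation of 400,000 samples per scenario, with a Beta share of mean 0.5, 0.7 or 0.9 (parameters summing to 10), gave 1.9% to 24.7% over medians of 0.005% to 0.05%. With parameters summing to 5 or 20 the minimum was 2.6% or 1.3%, and the maximum stayed close to 25%.

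**Other reading of LLOQ/2.** If 0.0005% were meant for both measures, inversion would occur for any Th1 of 0.001% or more with a total below 0.02%, a wider band.

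**Timing.** No arithmetic applies. SAP 6.2 allows change without limit. SAP 1 places group-unblinded looks before the final analysis. Protocol 11.8 says results of additional interim analyses will not affect later immunogenicity assessments, but names no cut-off. The Protocol's Amendment 4 rationale records that a group-unblinded interim with immunogenicity data had already been reviewed by April 2019, without saying whether ICS was in it.

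**The case against.** The case for leaving the text alone has real weight.

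- *Endpoint status.* Protocol Tables 3 and 7 make ICS secondary for Th1/Th2 subtyping and list the broader CD4/CD8 cytokine readout as exploratory, although Protocol 2.1.2 describes the secondary endpoint more widely. The 0.02% cut-off applies only to the total. A reader might infer that the mismatch distorts the Th1/Th2 profile. It does not, because those two share a cut-off.
- *Size.* The inversion is below 2-fold and confined to a narrow band. Total and Th1 appear in separate outputs, and the planned scatterplot is Th1 against Th2. A reader might blame the 20-fold gap between the cut-offs. Any unequal pair produces inversions; a larger gap only widens the band.
- *Looks.* A reader might count every scheduled group-unblinded analysis as a chance to see ICS by arm. SAP 6.1 says not every assay enters every analysis. Toddler cellular blood is scheduled only on Days 1 and 29, so the Day 8 look would hold almost only baseline ICS. The Cohort 0 analysis concerns adults.
- *Intent.* A reader might infer that the sponsor plans to reset cut-offs after seeing arm results. The SAP speaks only of progressing insight, in a bullet about an assay with no validated limit, and that can mean assay knowledge. Protocol 5 and SAP 1.5 restrict who sees interim results. Also, the sentence directly follows the Th1/Th2 cut-off and may not cover 0.02%, though that value is labelled provisional too.
- *Deferred detail.* Technical ICS calculations for the graphs are left to the DPS, which is not available here.

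These points limit the size of the problem. They do not restore the part-whole order or supply a freeze point: the substitution rule stands in the SAP itself, and the Protocol's general statement fixes no number.

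**Conclusion.** The point holds within limits. As written, SAP 6.2 can report a CD4 Th1 value above the CD4 total that contains it whenever 0.01% < Th1 ≤ total < 0.02%, by less than 2-fold. That result needs only the SAP's definitions, its two cut-offs, the reading of LLOQ/2 as half the cut-off, and measured Th1 no larger than measured total. The frequency of about 2% to 25% of samples rests on the assumed lognormal spread, medians and IFN-gamma shares, and its lower end on how much the share varies. It is an illustration, not a forecast.

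The imputed number is itself undefined, since LLOQ/2 refers to a limit the SAP says does not exist. Separately, the cut-offs have no freeze point although group-unblinded analyses that may include ICS precede the final one. This is an absence of protection; the documents do not show that any cut-off was changed after arm results were seen. All ICS results are descriptive, so no error rate is affected. What suffers is the internal consistency of the cellular tables and plots and a reader's ability to trust the thresholds.

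**What to change.** Amend SAP 6.2 in two places.

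(a) Apply one handling rule to the CD4 total and Th1. Either use the same cut-off for both, or summarise and plot measured values with the cut-off drawn as a reference line. If a common cut-off other than 0.001% is chosen, apply it to Th2 as well so that Th1 and Th2 stay comparable. State the actual number substituted in place of LLOQ/2. Exempting from substitution only those totals with a high Th1 is not a good alternative, because the handling of one outcome would then depend on another.

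(b) Replace the open-ended sentence with, for example: *ICS cut-offs are recorded and dated before the first group-unblinded Cohort 1 analysis that includes ICS. Any later change is applied to both arms and all time points, and results under the original cut-off are shown beside it.* If that analysis has already taken place, document the values used and when they were set.

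The cost is SAP wording, minor programming and, if a cut-off later changes, one extra set of ICS tables. No further data or samples are needed.

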### 6.3. Immune Response Analysis

No formal hypothesis on immunogenicity will be tested.

#### 6.3.1. Immunogenicity against the insert:

##### 6.3.1.1. Humoral assays

For VNA and ELISA assays following results will be calculated: N, geometric mean§ and corresponding 95% CI of the actual values and fold increases from baseline will be tabulated and graphically presented. §calculate the mean and corresponding 95%CI of the log2 transformed values, back-transform this mean [i.e. 2mean] and CI [i.e. 2CI].

Tables showing fold increases will also present the percentage of subjects with an x-fold increase (for several values of x).

Actual values and fold changes from baseline are tabulated and shown as dot plots with dots for subject values, and the corresponding geometric mean and 95% CI per time point for each assay. In addition, GMT plots over time, combining the regimens in one graph (without individual subject dots) will also be created.

Subject profiles of the actual values over time will be graphically presented.

Reverse distribution curves of the actual values are provided for selected time points.

In the graphs, original values will be displayed on the log2 scale.

A scatterplot with the VNA versus ELISA will be provided for the most important time points. In these scatter-plots the actual values will be shown, even if they are below the LLOQ, but the LLOQ cut-off will be visualized in the graph per assay if some values are below LLOQ.

### 6.3.1.2. Cellular assays

For **ICS** and **PBMC secreted** cytokines (if available) analyses may include:

Total Cytokine response: the % of subsets expressing at least IFN $\gamma$ , TNF $\alpha$  or IL2 will be calculated for CD4 and CD8, separately.

Tables with the corresponding descriptive statistics will be provided.

Subject profiles of the actual values over time will be graphically presented.

Actual values are shown as box plots with dots for subject values, and the corresponding median and the first and third quartile (Q1, Q3) per time point for each assay.

In addition, box plots over time, combining the regimens in one graph (without individual subject dots) will also be created.

For all cytokine combinations (IFN $\gamma$  and/or TNF $\alpha$  and/or IL2) pie charts reflecting the distribution of each of the cytokine combinations (the proportion of a specific cytokine combination of the CD4 or CD8 T-cells secreting at least one cytokine) and bar charts reflecting the median magnitude of each combination will be graphically presented. Tables with the corresponding descriptive statistics will be provided.

Th1 and Th2: Th1 is defined as all CD4+ IFN $\gamma$ + and Th2 as all CD4+ IL4+ cells. Subject profiles and graphs of the actual values over time (box-plot type) will be created. In addition, at time points of interest, scatterplots of Th1 vs Th2 might be created.

For the graphs, original values will be displayed on the log10 scale.

The technical details for the calculation of the ICS values to be used in the graphs will be outlined in the DPS.

For **ELISpot**, if available following results will be calculated: N, median, quartiles and range of the actual values will be tabulated and graphically presented.

Tables with the corresponding descriptive statistics will be provided.

Subject profiles of the actual values over time will be graphically presented.

Actual values are shown as box plots with dots for subject values, and the corresponding median and interquartile range per time point for each assay. In addition, box plots over time, combining the regimens in one graph (without individual subject dots) will also be created. For the graphs, original values will be displayed on the log10 scale.

### 6.3.2. Immunogenicity against the vector

For VNA, if available following statistics will be calculated: N, geometric mean§(see above for the calculation) and corresponding 95% CI of the actual values.

Scatterplots with the assays against the vector versus the assays against the inserts might be created for the most important time points. In these scatter-plots the actual values will be shown, even if they are below the LLOQ.

## 7. RSV INFECTIONS

In case of a severe LRTI being present in Cohort 1, then all potential cases of RSV infection will be summarized in the following two categories and based on their severity (severe/ non-severe).

- Suspected RSV infection: subject has persistent (>48 hours) clinical symptoms of rhinitis (sneezing or runny nose or congestion) and persistence (>24 hours) of one or more of the following: cough, abnormal breathing, fever, lethargy or decreased appetite. Occurrence of this combination of symptoms in any subject would trigger collection of a nasal turbinate sample.
- Confirmed RSV infection: subject with suspected RSV infection and positive for RSV on the basis of RT-PCR conducted centrally.

**ATTACHMENTS****Attachment 1: Guidance for Industry: Toxicity Grading Scale for Healthy Adult and Adolescent Volunteers Enrolled in Preventive Vaccine Clinical Trials**

The laboratory values provided in the tables below serve as guidelines and are dependent upon institutional normal parameters. Institutional normal reference ranges should be provided to demonstrate that they are appropriate.

If a laboratory value falls within the grading as specified below but also within the local laboratory normal limits, the value is considered as normal.

Serum *	Mild (Grade 1)	Moderate (Grade 2)	Severe (Grade 3)	Potentially Life Threatening (Grade 4)**
Sodium – Hyponatremia mEq/L	132 – 134	130 – 131	125 – 129	< 125
Sodium – Hypernatremia mEq/L	144 – 145	146 – 147	148 – 150	> 150
Potassium – Hyperkalemia mEq/L	5.1 – 5.2	5.3 – 5.4	5.5 – 5.6	> 5.6
Potassium – Hypokalemia mEq/L	3.5 – 3.6	3.3 – 3.4	3.1 – 3.2	< 3.1
Glucose – Hypoglycemia mg/dL	65 – 69	55 – 64	45 – 54	< 45
Glucose – Hyperglycemia Fasting – mg/dL Random – mg/dL	100 – 110 110 – 125	111 – 125 126 – 200	>125 >200	Insulin requirements or hyperosmolar coma
Blood Urea Nitrogen BUN mg/dL	23-26	27 – 31	> 31	Requires dialysis
Creatinine – mg/dL	1.5 – 1.7	1.8 – 2.0	2.1 – 2.5	> 2.5 or requires dialysis
Calcium – hypocalcemia mg/dL	8.0 – 8.4	7.5 – 7.9	7.0 – 7.4	< 7.0
Calcium – hypercalcemia mg/dL	10.5 – 11.0	11.1 – 11.5	11.6 – 12.0	> 12.0
Magnesium – hypomagnesemia mg/dL	1.3 – 1.5	1.1 – 1.2	0.9 – 1.0	< 0.9
Phosphorous – hypophosphatemia mg/dL	2.3 – 2.5	2.0 – 2.2	1.6 – 1.9	< 1.6
CPK – mg/dL	1.25 – 1.5 x ULN***	1.6 – 3.0 x ULN	3.1 – 10 x ULN	> 10 x ULN
Albumin – Hypoalbuminemia g/dL	2.8 – 3.1	2.5 – 2.7	< 2.5	--
Total Protein – Hypoproteinemia g/dL	5.5 – 6.0	5.0 – 5.4	< 5.0	--

Serum *	Mild (Grade 1)	Moderate (Grade 2)	Severe (Grade 3)	Potentially Life Threatening (Grade 4)**
Alkaline phosphate – increase by factor	1.1 – 2.0 x ULN	2.1 – 3.0 x ULN	3.1 – 10 x ULN	> 10 x ULN
Liver Function Tests –ALT, AST increase by factor	1.1 – 2.5 x ULN	2.6 – 5.0 x ULN	5.1 – 10 x ULN	> 10 x ULN
Bilirubin – when accompanied by any increase in Liver Function Test increase by factor	1.1 – 1.25 x ULN	1.26 – 1.5 x ULN	1.51 – 1.75 x ULN	> 1.75 x ULN
Bilirubin – when Liver Function Test is normal; increase by factor	1.1 – 1.5 x ULN	1.6 – 2.0 x ULN	2.0 – 3.0 x ULN	> 3.0 x ULN
Cholesterol	201 – 210	211 – 225	> 226	---
Pancreatic enzymes – amylase, lipase	1.1 – 1.5 x ULN	1.6 – 2.0 x ULN	2.1 – 5.0 x ULN	> 5.0 x ULN

\* The laboratory values provided in the tables serve as guidelines and are dependent upon institutional normal parameters. Institutional normal reference ranges should be provided to demonstrate that they are appropriate.

\*\* The clinical signs or symptoms associated with laboratory abnormalities might result in characterization of the laboratory abnormalities as Potentially Life Threatening (Grade 4). For example, a low sodium value that falls within a grade 3 parameter (125-129 mE/L) should be recorded as a grade 4 hyponatremia event if the subject had a new seizure associated with the low sodium value.

\*\*\*"ULN" is the upper limit of the normal range.

Hematology *	Mild (Grade 1)	Moderate (Grade 2)	Severe (Grade 3)	Potentially Life Threatening (Grade 4)
Hemoglobin (Female) - gm/dL	11.0 – 12.0	9.5 – 10.9	8.0 – 9.4	< 8.0
Hemoglobin (Female) change from baseline value - gm/dL	Any decrease – 1.5	1.6 – 2.0	2.1 – 5.0	> 5.0
Hemoglobin (Male) - gm/dL	12.5 – 13.5	10.5 – 12.4	8.5 – 10.4	< 8.5
Hemoglobin (Male) change from baseline value – gm/dL	Any decrease – 1.5	1.6 – 2.0	2.1 – 5.0	> 5.0
WBC Increase - cell/mm 	10,800 – 15,000	15,001 – 20,000	20,001 – 25,000	> 25,000
WBC Decrease - cell/mm 	2,500 – 3,500	1,500 – 2,499	1,000 – 1,499	< 1,000
Lymphocytes Decrease - cell/mm 	750 – 1,000	500 – 749	250 – 499	< 250
Neutrophils Decrease - cell/mm 	1,500 – 2,000	1,000 – 1,499	500 – 999	< 500
Eosinophils - cell/mm 	650 – 1500	1501 - 5000	> 5000	Hypereosinophilic
Platelets Decreased - cell/mm 	125,000 – 140,000	100,000 – 124,000	25,000 – 99,000	< 25,000
PT – increase by factor (prothrombin time)	1.0 – 1.10 x ULN**	1.11 – 1.20 x ULN	1.21 – 1.25 x ULN	> 1.25 ULN
PTT – increase by factor (partial thromboplastin time)	1.0 – 1.2 x ULN	1.21 – 1.4 x ULN	1.41 – 1.5 x ULN	> 1.5 x ULN
Fibrinogen increase - mg/dL	400 – 500	501 – 600	> 600	--
Fibrinogen decrease - mg/dL	150 – 200	125 – 149	100 – 124	< 100 or associated with gross bleeding or disseminated intravascular coagulation (DIC)
International Normalized Ratio (INR)***	1.1 to < 1.5 x ULN	1.5 to < 2.0 x ULN	2.0 to < 3.0 x ULN	≥ 3.0 x ULN

\* The laboratory values provided in the tables serve as guidelines and are dependent upon institutional normal parameters. Institutional normal reference ranges should be provided to demonstrate that they are appropriate.

\*\* "ULN" is the upper limit of the normal range.

\*\*\*: For INR, the values in the table are based on the Division of AIDS Table for Grading the Severity of Adult and Pediatric Adverse Events, 2014 (version 2.0)

Urine *	Mild (Grade 1)	Moderate (Grade 2)	Severe (Grade 3)	Potentially Life Threatening (Grade 4)
Protein	Trace	1+	2+	Hospitalization or dialysis
Glucose	Trace	1+	2+	Hospitalization for hyperglycemia
Blood (microscopic) - red blood cells per high power field (rbc/hpf)	1 - 10	11 - 50	> 50 and/or gross blood	Hospitalization or packed red blood cells (PRBC) transfusion

\* The laboratory values provided in the tables serve as guidelines and are dependent upon institutional normal parameters. Institutional normal reference ranges should be provided to demonstrate that they are appropriate.

Vital Signs *	Mild (Grade 1)	Moderate (Grade 2)	Severe (Grade 3)	Potentially Life Threatening (Grade 4)
Fever (°C) ** (°F) *	38.0 – 38.4 100.4 – 101.1	38.5 – 38.9 101.2 – 102.0	39.0 – 40 102.1 – 104	> 40 > 104
Tachycardia - beats per minute	101 – 115	116 – 130	> 130	ER visit or hospitalization for arrhythmia
Bradycardia - beats per minute***	50 – 54	45 – 49	< 45	ER visit or hospitalization for arrhythmia
Hypertension (systolic) - mm Hg	141 – 150	151 – 155	> 155	ER visit or hospitalization for malignant hypertension
Hypertension (diastolic) - mm Hg	91 – 95	96 – 100	> 100	ER visit or hospitalization for malignant hypertension
Hypotension (systolic) – mm Hg	85 – 89	80 – 84	< 80	ER visit or hospitalization for hypotensive shock
Respiratory Rate – breaths per minute	17 – 20	21 – 25	> 25	Intubation

\* Subject should be at rest for all vital sign measurements.

\*\* Oral temperature; no recent hot or cold beverages or smoking.

\*\*\* When resting heart rate is between 60 - 100 beats per minute. Use clinical judgement when characterizing bradycardia among some healthy subject populations, for example, conditioned athletes.

